7.3 Data Handling Convention for Missing Data

Efficacy:

For efficacy summaries, only observed data will be used. Missing efficacy data will not be imputed.

Adverse events:

If severity or relationship should be missing, the most severe or more related category will be imputed for the summary.

Other safety:

For safety summaries, only observed data will be used. Unless otherwise specified, missing safety data will not be imputed.

8 STATISTICAL METHODOLOGY

8.1 Study Subjects

8.1.1 Subject Disposition

Subject disposition will be summarized on the SAF and listed on the enrolled subjects.

8.1.2 Analysis Populations

Analysis populations will be summarized and listed on the enrolled subjects. The listing will include the inclusion and exclusion criteria deviation at Day 1.

8.1.3 Study Drug Exposure

Exposure data will be summarized and listed on the SAF.

IMP compliance data will be listed on the SAF.

8.1.4 Demographic and Other Baseline Characteristics

The following demographic and other baseline characteristics will be used.

	Categorical	Descriptive
Sex	Male, Female	
Age at informed consent (years)		Yes
Ethnicity	Hispanic or Latino, Not Hispanic or Latino, Not Reported, Unknown	
Race	White, Black or African American, Asian - Japanese, Asian - Not Japanese, American Indian or Alaska Native, Native Hawaiian or Other Pacific Islander	

Demographic and other baseline characteristics will be summarized and listed on the SAF.

8.1.5 ALSFRS-R score

The total ALSFRS-R score will be descriptively summarized by analysis visit on the SAF.

ALSFRRS-R score of each item, domain and total score will be listed on the SAF.

8.1.6 Event of death, tracheostomy or constant use of an assisted ventilator

Event of death, tracheostomy or constant use of an assisted ventilator (≥ 23 hours/day) will be summarized by the number and the percentage of events on the SAF. The number of subjects in whom any of these events occurred will also be summarized.

All data will be listed on the SAF.

8.2 Safety Assessments

All safety assessments will be performed on the SAF.

8.2.1 Adverse Events

Overall occurrence of Treatment-emergent adverse events (TEAE) will be summarized using the following categories.

- Subjects with at least one TEAE
- Subjects with at least one adverse drug reaction
- Subjects with at least one TESAE
- Subjects with at least one serious adverse drug reaction
- Subjects with at least one TEAE leading to discontinuation of study drug
- Subjects with AE leading to death

The following summaries will also be presented.

- TEAEs by SOC and PT
- TEAEs by SOC, PT and severity
- TEAEs by SOC, PT and causality
- TEAEs leading to discontinuation of study drug by SOC and PT

- TEAEs leading to death by SOC and PT
- Adverse drug reactions by SOC and PT
- Adverse drug reactions by SOC, PT and severity
- TESAEs by SOC and PT
- Serious adverse drug reactions by SOC and PT

These will be subject-based summaries - multiple occurrences of the event with the same SOC and/or PT within a subject will be counted once in the summaries by SOC and PT; multiple occurrences of the event with the same SOC and/or PT but different severity within a subject will be counted once in the maximum severity category (severe > moderate > mild) and/or maximum drug relationship category (reasonable possibility/no reasonable possibility).

All TEAEs, Adverse drug reactions and TESAEs will be listed.

8.2.2 Vital signs

Absolute values will be summarized for the following parameters by analysis visit.

- Systolic blood pressure (mmHg)
- Diastolic blood pressure (mmHg)
- Heart rate (beats/min)
- Respiratory Rate (beats/min)
- Body temperature (°C)

For overall evaluation, number and percentage will be presented by analysis visit.

All data (including overall evaluation) will be listed.

8.2.3 Orthostatic vital signs

Absolute values will be summarized for the following parameters by analysis visit.

- Systolic blood pressure (mmHg)
- Diastolic blood pressure (mmHg)
- Heart rate (beats/min)

Statistical Analysis Plan
Protocol No. MT-1186-A-301

Mitsubishi Tanabe Pharma Corporation

For overall evaluation, number and percentage will be presented by analysis visit.

All data (including overall evaluation) will be listed.

8.2.4 Pregnancy test

Pregnancy test will be listed.

8.2.5 Physical Examinations

Physical examination will be listed.

8.2.6 12-Lead ECGs

Absolute values will be summarized for the following parameters by analysis visit.

- RR (msec)
- Heart rate (beats/min)
- QRS (msec)
- QT (msec)
- QTcB (msec)
- QTcF (msec)

For overall evaluation, number and percentage will be presented by analysis visit. The percentage of subjects with values outside pre-defined limits will be summarized by analysis visit.

All data (including overall evaluation) will be listed.

8.2.7 Body weight

Absolute values will be summarized and listed by analysis visit.

8.2.8 Laboratory Tests

All data will be listed.

Below is a list of the laboratory test.

Laboratory Test	Parameters
Hematology	RBC count, hemoglobin, hematocrit, WBC count, platelet count
Biochemistry	Albumin, total protein, AST, ALT, LDH, ALP, total bilirubin, direct bilirubin, γ -GTP, CK, total cholesterol, triglycerides, BUN, bicarbonate, glucose, creatinine, uric acid, Na, K, Cl, Ca
Urinalysis	Protein, glucose, occult blood, urobilinogen, leukocytes, bilirubin

8.2.9 C-SSRS

For the C-SSRS, the number and percentage of subjects who exhibited suicidal ideation or behavior for each C-SSRS scale will be presented by analysis visit.

All data will be listed.

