7.4 Exclusion criteria

Subjects who meet any of the following criteria will be excluded from the study:

1. Subjects of childbearing potential who are not tested negative by a pregnancy test, subjects who are breastfeeding, and subjects who are unwilling to use a highly effective method of contraception from the Visit #1 until 3 months after the last dose of study medication. Refer to Attachment 2 for additional contraceptive information.
2. Subjects who have a significant risk of suicide. Subjects with any suicidal behavior or suicidal ideation of type 4 (active suicidal ideation with some intent to act, without a specific plan) or type 5 (active suicidal ideation with

specific plan and intent) based on the C-SSRS at Week 96 of the A03 study or at Week 48 of the A04 study.

3. Subjects who are not eligible to continue in the study, as judged by the Investigator.
4. Subjects who cannot receive drugs orally or via PEG/RIG.

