10.7 Columbia-Suicide Severity Rating Scale (C-SSRS)

The clinician will attend a certified rater training for the C-SSRS.

The C-SSRS is a clinician-rated instrument that captures the occurrence, severity, and frequency of suicide-related ideations and behaviors during the assessment period. The C-SSRS must be administered by appropriately trained site personnel. Suicidal ideation is classified on a 5-item scale: 1 (wish to be dead), 2 (nonspecific active suicidal thoughts), 3 (active suicidal ideation with any methods [not plan] without intent to act), 4 (active suicidal ideation with some intent to act, without specific plan), and 5 (active suicidal ideation with specific plan and intent). The C-SSRS also captures information about the intensity of ideation, specifically the frequency, duration, controllability, deterrents, and reasons for the most severe types of ideation. Suicidal behavior is classified on a 5-item scale: 0 (no suicidal behavior), 1 (preparatory acts or behavior), 2 (aborted attempt), 3 (interrupted attempt), and 4 (actual attempt). More than 1 classification can be selected provided they represent separate episodes. For actual attempts only, the actual or potential lethality is classified for the initial, most lethal, and most recent attempts. C-SSRS assessments are presented in Appendix 3.

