2.1.1 Primary Safety Assessment(s)

- (1) Adverse events (AEs) and adverse drug reactions (ADRs)
- (2) Physical examination, including neurological examination
- (3) Body weight
- (4) 12-lead ECG
- (5) Vital signs (heart rate, respiratory rate, systolic/diastolic blood pressure and axillary, oral or tympanic temperature [the method should be consistent throughout the study])
- (6) Safety laboratory tests (hematology, blood biochemistry, urinalysis, pregnancy test)
- (7) Columbia Suicide Rating Scale (C-SSRS)

Statistical Analysis Plan
Protocol No. MT-1186-A-301

Mitsubishi Tanabe Pharma Corporation

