7.1.3 Safety Assessments

7.1.3.1 Adverse Events

Adverse events will be coded according to the MedDRA version 25.0.

(1) Treatment Emergent Adverse Events/ Treatment Emergent Serious Adverse Events (TEAEs/TEsAEs)

An AE/SAE is classified as treatment emergent if it newly occurred after the first dose of investigational product or if a pre-dose event increases in severity following the first dose of investigational product.

(2) Adverse Drug Reaction

A TEAE is considered “adverse drug reaction” if it has been assessed as having a “reasonable possibility” in relationship to the investigational product.

(3) Time to Adverse Events

Time to Adverse Events occurrence (days) = AE start date – date of first administration in this study + 1

If the date of onset of an adverse event or the first administration is indeterminate, time to adverse events occurrence is not calculated.

(4) Duration of Adverse Events

Duration of Adverse Events (days) = AE stop date – AE start date + 1

If the adverse event is ongoing at the end of study, duration of adverse events is not calculated.

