7.2 Analysis Visit Definitions

Week 96 of Study MT-1186-A03 or Week 48 of Study MT-1186-A04 is defined as Day 1 of this study. By-visit summaries will be based on analysis visit. Any data out of the window will not be used. If there are multiple data of the same item within a window, the latest data will be used for analysis.

Tests	Analysis visit	Nominal time point	Analysis time window
Vital signs 12-lead ECG	Week 24	24 weeks after initiation of study treatment	Nominal time point \pm 30D
Body weight ALSFRS-R C-SSRS	EOS/ET	At the end of the study and early discontinuation	Nominal time point will be used.

In this study, because Edaravone became commercially available and the study was terminated, no subjects reached Week 24. Based on this condition, the sponsor decided in the DRM held on 20 Sep that only "EOS/ET" is used for analyses.

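### For C-SSRS ideation types 1-3, the planned summary cannot separate ideation continuing from before Day 1 from ideation that is new or worse after Day 1

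*SAP*

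**What the plan says.** - **Role of the scale.** Protocol 5.2.1 and SAP 2.1.1 both list the C-SSRS among the primary safety assessments.
- **Entry.** Protocol 7.4, exclusion 2, removes anyone showing "any suicidal behavior or suicidal ideation of type 4 (active suicidal ideation with some intent to act, without a specific plan) or type 5" at Week 96 of A03 or Week 48 of A04. It also opens with a general clause, "Subjects who have a significant risk of suicide", and exclusion 3 leaves room for investigator judgement.
- **What remains admissible by rule.** Protocol 10.7 defines the lower ideation types as "1 (wish to be dead), 2 (nonspecific active suicidal thoughts), 3 (active suicidal ideation with any methods [not plan] without intent to act"). None of these is named as an exclusion.
- **Baseline.** SAP 7.2 makes that parent-study visit Day 1 of this study. The schedules in both documents show a C-SSRS there, carried over and not repeated.
- **Planned summary.** SAP 8.2.9: "the number and percentage of subjects who exhibited suicidal ideation or behavior for each C-SSRS scale will be presented by analysis visit". All C-SSRS data are also listed. Protocol 15.3.3.4 plans the same kind of count. Neither defines new or worsened ideation.
- **Visits.** SAP 7.2 records that no subject reached Week 24 and that "the sponsor decided in the DRM held on 20 Sep that only" the EOS/ET visit is used for analyses. SAP 9.2 still names Day 1, Week 24 and EOS/ET as visits for the outputs.
- **Contrast with adverse events.** SAP 7.1.3.1 counts an event as treatment-emergent if it is new after the first dose or "if a pre-dose event increases in severity following the first dose of investigational product".

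**The concern.** In a long-term safety extension, the useful question about suicidality is how many subjects developed it or got worse after entering. The SAP answers that question for adverse events but not for the C-SSRS, where it plans only a count at each visit. Some subjects may enter with type 1, 2 or 3 ideation. If so, the EOS/ET count mixes those who continued as before with those who changed, and the summary reports one number for both.

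The scale is not there as a formality. Protocol 4.2 reports one completed suicide among the 185 subjects of study A01. That says nothing about how common types 1-3 are in this study, but it is a reason to want the C-SSRS result to be interpretable.

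**Working it through.** The plan states no C-SSRS rate, power or precision, so it has no figure to reproduce. The check compares the passages and then asks what the planned counts can determine.

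**1. What an EOS/ET rating covers.** The example form in Protocol Appendix 3 is the since-last-visit version. A rating therefore covers the interval since the previous assessment. Ideation that had ended by Day 1 should not be counted at EOS/ET. Ideation that continued or recurred after Day 1 is counted, and so is ideation that first appeared after Day 1.

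**2. What two visit totals determine.** Let N be the subjects rated at both visits, *a* those with any ideation at Day 1, and *b* those with any ideation at EOS/ET. The number with new ideation (none at Day 1, some later) then satisfies

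max(0, b − a) ≤ new ≤ min(b, N − a),

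with N − a subjects at risk of new ideation. N = 30 is the approximate planned number (Protocol 15.1). The values of *a* and *b* are assumptions.

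| Assumed a = b | At risk, N − a | New cases | Percentage |
|---|---|---|---|
| 0 | 30 | 0 exactly | 0% |
| 1 | 29 | 0 to 1 | 0 to 1/29 = 3.4% |
| 3 | 27 | 0 to 3 | 0 to 3/27 = 11.1% |
| 5 | 25 | 0 to 5 | 0 to 5/25 = 20.0% |

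Within each row the two visit totals are identical across the whole range. When a = 0, both bounds equal *b*, so the planned count is already the new-case count.

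**3. Without a Day 1 column.** If only EOS/ET is printed, three positive subjects appear as 3/30 = 10.0%. The denominator is the whole analysis set under SAP 6.1. The number new or worse could be anything from 0/30 to 3/30.

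**4. If the counts are given by category.** The wording in 8.2.9 may mean a count for each ideation type. Take an assumed case: three subjects at type 1 on Day 1, then two at type 1 and one at type 3 at EOS/ET.

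- The type 3 subject must be new or worse, because nobody was at type 3 on Day 1. Category counts do reveal that.
- They do not show which. If the same three subjects are positive at both visits, there are 0 new and 1 worsened. If three different subjects are positive, there are 3 new and 0 worsened.
- The total new or worse still ranges from 1 to 3.

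**5. Behavior and types 4-5.** Entry sets these to zero at Day 1 in a correctly enrolled subject. Any occurrence at EOS/ET is then new or worse by construction. The ambiguity is confined to types 1-3.

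**The case against.** The strongest reply is that nothing is lost. All C-SSRS data are listed, there are about 30 subjects, and only EOS/ET is used after Day 1, so each subject's change is two entries in a listing. This largely stands and is the main reason the point is small. It depends on the listing including Day 1. It also leaves each reader to decide what counts as worsened, so there is no planned new-or-worsened result.

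A second reply is that the adverse event tables will capture it. Protocol 13 has investigators ask about adverse events at each visit, 13.1 treats aggravation as a new event, and 13.5 covers clinically significant abnormal assessments. New or worse ideation fits that general wording. However, 10.7, unlike 10.2, 10.3 and 10.5, has no sentence sending a finding to adverse event reporting, so capture is possible but not assured.

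A third is that Day 1 is not a drug-free baseline: subjects roll over from oral edaravone studies and there is no control arm. This is correct. A change from Day 1 cannot be attributed to the drug. It limits what the added table means, though it is no reason to prefer counts that show no change at all.

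Fourth, vital signs, ECG and weight are also summarized as absolute values by visit, so the C-SSRS plan is in keeping with a descriptive study. That is fair: there is no contradiction or calculation error here.

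**Conclusion.** For ideation types 1-3, the planned C-SSRS summary cannot tell continuing ideation from ideation that is new or worse after Day 1. The size depends wholly on how many subjects had ideation at Day 1, which the documents do not give. It is nil if none did, and the illustrative ranges above rest on assumed counts and on both ratings being available.

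A reader might infer more than this, and the documents do not support it:

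- **That serious suicidality could be hidden.** Behavior and types 4-5 are excluded at Day 1, so their appearance at EOS/ET is already unambiguous in correctly enrolled subjects.
- **That the table counts whatever ideation happens to be present on the visit day.** The form covers the interval since the last visit.
- **That a move from type 1 to type 3 could never show in a summary.** If counts are given by category and a Day 1 column is printed, it sometimes would.
- **That the entry rule is at fault.** The point concerns tabulation only.

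This is an optional-to-modest reporting improvement.

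**What to change.** Add to SAP 8.2.9:

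1. A cross-tabulation of ideation type (0-5, with 0 for none) at Day 1, the parent Week 96 or Week 48 rating, against the most severe type after Day 1.
2. The number and percentage with **new** ideation. The denominator is subjects with none at Day 1 and a post-Day-1 rating.
3. The number and percentage with **worsened** ideation (a higher type than at Day 1). The denominator is subjects with both ratings.
4. A note that new and worsened are relative to Day 1 of this study, not to a drug-free baseline.
5. A statement that the Day 1 C-SSRS is used for this table despite the restriction to EOS/ET in SAP 7.2. The visit list in SAP 9.2 should be reconciled with that restriction.

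Keep the planned visit counts and the listing, and make sure the listing shows Day 1. The cost is a short SAP addition and one extra table from ratings already scheduled. The table will be sparse with about 30 subjects. If the data have already been fixed, Protocol 15 provides for describing the addition in the study report.

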9 DATA PRESENTATION CONVENTIONS

9.1 Number of Digits to Report

Statistic	Specification	Apply to
Minimum, Maximum	Same number of DPs as provided in the datasets	All original data (i.e. non-derived)
	see section 7.1	All derived data
Mean, SD, Median	One more DP than above	All
Percentages ¹	1 DP	All

¹ Percentages: use 1 place beyond the decimal point, except for the following cases:

If the percentage is equal to 0, then not shown as "(0)" but left blank

If the percentage is equal to 100, then shown as "(100)" without a decimal

9.2 Visit to Report

Visit for TFLs:

- Day 1
- Week 24
- EOS/ET

10 CHANGE FROM THE PROTOCOL

- The time point when the events of death, tracheostomy, and constant use of assisted

Statistical Analysis Plan
Protocol No. MT-1186-A-301

Mitsubishi Tanabe Pharma Corporation

ventilator (23 hours/day or more) are summarized was changed from each visit to only EOS/ET, because the data of the events is collected only at EOS/ET.

11 SOFTWARE

All statistical analyses will be performed using SAS version 9.4 or higher.

